The facilitator is an experienced practitioner who provides individual and group parenting support to Children and Families, and has been delivering the Group since its creation in 2016. Prior to developing the Group, he received training in running engaging and meaningful groups with men. The Group is co-delivered with another 1-2 facilitators, who could be other parenting practitioners but are ideally men who have previously received the Group intervention themselves, and who are trained by the lead facilitator to co-deliver the Group.

The Group creates a space for male carers to connect with others to talk about their parenting concerns and achievements, while also learning about child development, and parenting techniques which focus on positive relationship management and conflict resolution. The Group aims to help fathers improve their relationship with their child and other people involved in the care of their child, including partners, co-parents, and social care professionals. To ensure relevant support is offered, the format and content of sessions were developed in collaboration with the fathers attending the programme.

Each Group is attended by approximately 16-20 fathers, with numbers varying slightly per cohort. After week four, the Group is closed to new members to ensure confidentiality of those attending and protect the initial bond between group members. Where the number of referrals exceeds the available spaces in the Group or where fathers do not attend, they will automatically be offered a place in the next available cohort.

A week before the start of each cohort fathers are invited to a coffee morning where they can meet the other members and the facilitator(s). This helps build an understanding of how the Group will work and creates a sense of familiarity for the fathers in relation to the venue. The venue is also chosen as a “neutral” space, such as a room in a Children’s Centre. Access to childcare for the duration of the sessions is also facilitated.

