The evaluation is being carried out in a single site, in collaboration with the delivery partner, Southwark Family Early Help, in the London Borough of Southwark. Eligible participants of the intervention Group will be male residents in the borough and have a carer role for a child aged 4–12-year-old with a social worker (fathers are also eligible if only the child is resident in the borough). Examples of male carers include fathers, step-fathers and grandfathers. Fathers will be referred to the Group via existing pathways in Southwark CSC. All those who accept taking part in the Fathers Group intervention during one of the three cohorts starting Autumn 2023, January 2024, and Spring 2024, are eligible to the study.

Fathers are usually referred to the Group by a CSC professional (e.g. social worker) but may also self-refer. The single exclusion criterion that would lead to a referral to the Group not being accepted, is if the lead parenting practitioner, in consultation with the social worker, identify that contact between the father and child is inexistent or deemed not to be in the child's best interest. Characteristics that might affect accessibility to the Group, such as fathers' disability or no fluency in English, are not exclusion criteria; in such cases, the local authority attempts to put in place the required support (e.g. interpreter). See Intervention Protocol for further detail on inclusion and exclusion criteria to the Group.

For fathers who live with a partner (regardless of biological and parental responsibility for the father's children), they will also be invited to the study and asked to complete a few questionnaires. For participating fathers who have a child aged 11–12-years-old, the child will also be invited to complete a questionnaire.

Key stakeholders in Southwark CSC, including team managers, social workers, clinicians, and commissioners, will be invited to a 1:1 interview to further explore issues of feasibility, acceptability and scalability of this intervention and a future large-scale trial.

Key stakeholders in other local authorities in the country will be invited to complete a survey asking about availability and interest in similar/ competing interventions, as well as about the acceptability and scalability of a future large-scale trial of this kind.

Research questions

This study will evaluate the Southwark Fathers Group to assess the feasibility of both delivering the

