Services available to fathers in this site and other local authorities – from interviews, survey, and literature review.

Note. CAPI= Child Abuse Potential Inventory, CORE-10= Clinical Outcomes in Routine Evaluation, PSS= Parental Stress Scale, SCORE-15= Describe your family, APQ= The Alabama Parenting Questionnaire, b-PSES= The brief-Parental Self Efficacy Scale, QCCS= Quality of Co-parental Communication Scale, CoPRS= Co-parenting Relationship Scale, SDQ= Strengths and Difficulties Questionnaire, WAST= Women Abuse Screening Potential, URICA= University of Rhode Island Change Assessment Scale.

Methods

Sample and recruitment

The study aims to recruit 48 male carers who take part in one of three cohorts of the Group starting Autumn 2023, January 2024, and Spring 2024, totalling 16 parents per Group. The intervention facilitator will share information about the upcoming Groups among referring social workers. They will be able to refer fathers between August 2023 and March 2024, and fathers will then be assigned to the next upcoming Group. Referrals will be received on a rolling basis from social workers throughout this period. Social workers will be contacted by the lead facilitator – this could

be either in person or over the phone or email, with the support of a written leaflet to share information about the study. Fathers of a 4–12-year-old with a social worker, who accepted taking part in the Group intervention during one of the three cohorts, are eligible to the study.

Once fathers agree to take part in the Group, the Group facilitator will ask for their verbal consent to pass their contact details to the research team. The Group facilitator will also give potential participants a leaflet containing summary information about the study. A member of the research team will then contact fathers to explain and invite them to the study. Consenting fathers will be asked to read a Participant Information Sheet (PIS), complete an Informed Consent Form (ICF) online and complete the baseline assessment. Fathers' consent will include their agreement to being contacted by the research team after completion of the Group. At the end of the 10-week programme the research team will contact participants again to ask for their participation in the post-treatment assessments. Fathers' agreement or refusal to take part in the study will not affect their involvement in the intervention programme.

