Detailed information about the programme content and the training requirements of Group facilitators will be collected from the delivery team.

Intervention delivery and fidelity

The delivery team will record and share session logs for all sessions of the three cohorts, to allow treatment description and testing of feasibility of fidelity checks.

48

September 2023 – July 2024.

Cost-evaluation data

Estimated costs of the Group will be obtained from the delivery partner.

N/A

2023 – 2024.

Care As Usual (including alternative and/or competing services) will be collected from interviews with fathers,

interviews with professionals, and local authorities' survey, as well as a literature search.

Analysis

Feasibility parameters (means, proportions and variance estimates) will be calculated, using data from self-report questionnaire measures, administrative and process data. The responses from the scoping survey with local authorities will be summarised in tabular form.

Interviews and focus groups with fathers and professionals will be audio-recorded, transcribed and pseudonymised prior to analysis. Transcripts will be analysed using framework analysis, which allows a combination of pre-defined and emergent categories (Parkinson et al., 2016; Ritchie & Spencer, 1994), using an adapted version of the Experience of Therapy and Research Interview (Midgley et al., 2014). The final report will describe the key themes using quotations to illustrate the findings.

The detailed analysis plan that follows is organised by research question (RQ), even though there is overlap between some of the questions and the indicators to answer them.

RQ1. Is it possible to recruit and retain participants to an evaluation of the Fathers Group and collect quality outcome data?

Key feasibility parameters will be calculated based on proportions and 95% confidence intervals (CIs). First, to test the feasibility of recruiting/consenting fathers to the study, we will calculate: (i) the proportion of cases with successful contact to invite to Group, from those referred (target referrals received $n = 80$); (ii) the proportion of cases agreeing to take part in Group and proportion attending first session, from those contacted (target recruited to Group $n = 60$, target attending $n = 54$); (iii) the proportion of cases consenting to enter study from those receiving the Group (target recruited to study $n = 48$).

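### The study consent rate in RQ1 is divided by fathers receiving the Group, although the study approach is made to fathers who accept a place, so it is not a proportion of those approached and will probably overstate recruitability

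*Protocol*

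**What the plan says.** Three parts of the protocol bear on this rate.

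- **Analysis, RQ1.** The recruitment cascade has a target at each step. Step (i) starts from 80 referrals. Step (ii) separates agreeing to join from attending the first session: "target recruited to Group $n = 60$, target attending $n = 54". Step (iii), with a target of 48, is "the proportion of cases consenting to enter study from those receiving the Group". Each proportion is to carry a 95% confidence interval.
- **Participants; Methods, Sample and recruitment.** Eligibility for the study rests on acceptance: "All those who accept taking part in the Fathers Group intervention during one of the three cohorts" are eligible. The approach begins at the same point: "Once fathers agree to take part in the Group, the Group facilitator will ask for their verbal consent to pass their contact details". With that permission, researchers call him, explain the study and invite him. Consent is followed by the baseline survey, which the Data collection table places in the week before the first session.
- **Compliance, Consent.** Contact about the study is attempted by telephone first, but follow-up contact may be made in person at the first session.

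The protocol nowhere defines receiving the Group.

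**The concern.** The denominator of step (iii) is settled after most consent decisions have been made, and by a different behaviour, namely turning up. That has two effects. Fathers who were eligible and invited, said no, and then did not attend disappear from the rate. Fathers who said yes and then did not attend are study recruits under the rest of RQ1, where baseline and post-treatment completion are calculated among those recruited with no attendance condition, yet they have no place in this denominator. The numerator then need not be a subset of the denominator, and a binomial confidence interval presumes that it is.

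The rate matters for what follows. The Research questions table lists recruitment rates to intervention and to study as an indicator of whether randomisation within one authority is feasible. The RQ5 analysis draws on recruitment flow and rates for its recommendation on a future trial. In a randomised trial consent comes before allocation, so the useful figure is consent among fathers offered the study, not among those who later attend.

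**Working it through.** **Inputs (Analysis, RQ1):** accepted a place 60; attended first session 54; recruited to study 48. The 48 agrees with Sample and recruitment: 3 cohorts × 16 = 48. The protocol states no consent percentage, so the rates below are those its targets imply.

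**Implied rates.** The Wilson 95% interval is [p + z²/2n ± z√(p(1−p)/n + z²/4n²)] / (1 + z²/n), with z = 1.96.

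- As written, with receiving read as attending: 48/54 = 88.9%. Interval: (0.8889 + 0.0356 ± 0.0911)/1.0711 = 77.8% to 94.8%.
- Among accepters: 48/60 = 80.0%. Interval: (0.8000 + 0.0320 ± 0.1062)/1.0640 = 68.2% to 88.2%.
- Difference: 8.9 percentage points.

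**How far this depends on the non-attenders.** The targets leave 60 − 54 = 6 accepters who do not attend. Let k of them consent; k is an assumption, shown over its full range.

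Case A: 48 attenders consent, plus k non-attenders.

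| k | Attenders only, 48/54 | Accepters, (48+k)/60 | All consenters over attenders, (48+k)/54 |
|---|---|---|---|
| 0 | 88.9% | 80.0% | 88.9% |
| 2 | 88.9% | 83.3% | 92.6% |
| 4 | 88.9% | 86.7% | 96.3% |
| 5 | 88.9% | 88.3% | 98.1% |
| 6 | 88.9% | 90.0% | 100.0% |

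Case B: 48 consenters in total, k of them non-attenders.

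| k | Attenders only, (48−k)/54 | Accepters, 48/60 | All consenters over attenders, 48/54 |
|---|---|---|---|
| 0 | 88.9% | 80.0% | 88.9% |
| 2 | 85.2% | 80.0% | 88.9% |
| 4 | 81.5% | 80.0% | 88.9% |
| 5 | 79.6% | 80.0% | 88.9% |
| 6 | 77.8% | 80.0% | 88.9% |

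**General form.** Let a be the consent rate among attenders and b that among non-attenders. The accepter rate is (54a + 6b)/60 = 0.9a + 0.1b, so the attender-only rate differs from it by a − (0.9a + 0.1b) = 0.1(a − b). Check: a = 48/54 and b = 0 gives 0.089. The attender-only rate is therefore too high whenever non-attenders are less willing to join the study than attenders, and slightly too low when they are more willing. If instead every consenter is counted over 54, the ratio is 60/54 = 1.11 times the accepter rate whatever the non-attenders do.

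**The case against.** The strongest reply is that nothing is lost. Step (ii) reports agreement and attendance separately, the process data record numbers contacted, consenting and attending, and the future-trial recommendation rests on the whole recruitment flow. The accepter rate could be worked out from those counts. That is true and limits the harm, but the parameter the protocol defines, and would report with an interval, is the other one.

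The reply also has some support in the text. Sample and recruitment describes the 48 as men who take part in a cohort, which fits a denominator of participants. Consent contact can occur at the first session, baseline can be completed there, and the Group stays open to new members until week four. Only fathers who allow their details to be passed on are approached. So consent before the start is the main route, not the only one, and reading receiving as 54 is an inference. It is the most natural inference, because step (ii) uses separate terms and targets for the 60 and the 54.

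Some stronger readings do not hold:

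- A reader might infer that the planned rate overstates consent by nine points. That needs none of the six non-attenders to consent. The documents do not say so, and with the numerator restricted to attenders the direction can reverse.
- A reader might carry the two rates forward to the number of fathers a future trial must approach. The protocol gives no trial size.
- Social workers may "refer fathers between August 2023 and March 2024", while process data are dated from September 2023, so a reader might infer that August referrals go uncounted. The dates do not exclude earlier referrals, and the process-data sample of about 80 matches the full referral target.
- Fathers who do not attend, or for whom there is no space, are told that "they will automatically be offered a place in the next available cohort". A reader might infer double counting, but nothing says a repeat offer is logged as a new case.

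**Conclusion.** The point stands as a mismatch between the denominator of step (iii) and the population that the protocol makes eligible and approaches. It holds whatever the non-attenders do. Overstatement of recruitability is probable, not certain: on the targets it is 8.9 points (88.9% against 80.0%) if no non-attender consents. With a numerator of attenders only, it shrinks as more of them consent. It becomes an understatement of 1.1 points at k = 6 in Case A, and of 0.4 or 2.2 points at k = 5 or 6 in Case B. These figures assume that receiving means attending the first session and that the cascade runs at its target values. The matter deserves correction because recruitment rates inform the recommendation on randomisation, and because the correction is one of wording.

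**What to change.** Define step (iii) as fathers consenting to the study divided by eligible fathers who accepted a Group place (target 48/60). Between acceptance and consent, show two intermediate counts: fathers who agreed to share their contact details, and fathers reached and invited by the research team. Losses at either step are recruitment losses too, and showing them lets a reader calculate the rate among those actually invited. Keep the rate among attenders as a secondary figure, with its numerator restricted to attenders, and say what counts as receiving the Group.

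The cost is revised wording and the two intermediate counts in the recruitment log. The downside is that the headline rate will probably look less favourable, by up to about 9 points on the targets.
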